6.2 Sample Size Re-assessment

Drop out and mortality rates from enrollment to the 3 months visit and the proportion of subjects with a reason for referral at the 3 months visit will be monitored on an ongoing basis to account for possible heterogeneity in the drop-out and mortality rate and in the proportion of subjects with a reason for referral across geographies. A sample size re-assessment may be performed in regions with mortality

and drop-out rates different than 10% or with a proportion of subjects with reasons for referral different than 30%. The sample size reassessment will be produced as explained below.

The data gathered from each region at the time of the sample size re-assessment from enrollment to the 3 months visit will be used to compute the observed mortality and drop-out rate at the 3 months visit ($rate_{exit_observed}$) and the proportion of subjects with a reason for referral at the 3 months visit ($prop_{referral_reason}$) as follows:

$$rate_{exit_observed} = \frac{\text{Number of deaths and drop out before the 3 months visit}}{\text{Number of subjects enrolled}}$$

$$prop_{referral_reason} = \frac{\text{Number of subjects with a reason for referral at the 3 months visit}}{\text{Number of subjects with a 3 months visit completed}}$$

In regions where the drop-out and mortality rate ($rate_{exit_observed}$) will differ from 10% or the proportion of subjects with a reason for referral ($prop_{referral_reason}$) will differ from 30%, the total number of subjects to be enrolled ($N_{enrolled}$) will be computed following the below two steps:

Step 1: the number of subjects expected at the 3 months visit, given $prop_{referral_reason}$ will be computed as the ratio between the required number of subjects with a reason for referral at the three months visit ($N_{reason_referral} = 54$) and the observed proportion of subjects with a reason for referral at the three months visit ($prop_{referral_reason}$):

$$N_{3months} = \frac{54}{prop_{referral_reason}}$$

Step 2: the number of subjects to be enrolled, given $rate_{exit_observed}$ will be computed as the expected number of subjects that will complete the three months visit and the observed proportion of subjects that did not drop-out or die between enrollment and the 3 months visit ($1 - rate_{exit_observed}$):

$$N_{enrolled_update} = \frac{N_{3months}}{1 - rate_{exit_observed}}$$

Therefore, in regions where the drop-out and mortality rate will differ from 10% or the proportion of subjects with a reason for referral will differ from 30%, the number of subjects to be enrolled will change from the assumed approximately 200 to $N_{enrolled_update}$, to ensure at least a 80% power to achieve a 95% confidence interval width of 25% when 70% of patients with a reason for referral at the three months visit will be referred.

[figure not shown]
7. Statistical Methods

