9.6. Follow-Up Visits

Table 3 below specifies permitted time windows for the required subject visits. Subject visit target dates and windows for each follow-up will be made available to the study site. Follow-up visit windows are based on days post-acute MI, and the follow-up visit can be performed either in person or via phone. If a subject visit fall outside the pre-specified window, a study deviation must be reported and the original follow-up schedule maintained for subsequent visits.

Data analyses will include follow-up visits, regardless of whether the visits occur within the time window. Therefore, a late visit is preferred over a missed visit but must be accompanied by a deviation.

Table 3: Follow-up windows

Study Follow-up Visit	Window (Calculated days post-acute MI)		
	Window Start (days post-MI)	Target (days post-MI)	Window End (days post-MI)
3 month	40	90	120
6 month	150	180	210
12 month	335	365	395

Complete a Subject Visit CRF for each follow-up visit.

At 3-month follow-up visit, LVEF will be assessed as per standard practice:

- As per Investigator's discretion, if the subjects have LVEF $\leq 40\%$ or meeting one of the referral criteria (sustained VT, cardiac or unexplained syncope, clinically significant palpitations, new onset bundle branch block, conduction abnormalities, or symptomatic bradycardia), the subjects can be referred for SCD risk stratification and management (EP Referred Group). If the referral does not take place, it is not a study deviation.
- If the subjects have LVEF $>40\%$ but $<50\%$ (between 41% - 49%), the subjects will remain in the Non-Referred Group.
- If the subjects have LVEF $\geq 50\%$, they shall be exited from the study.

For the Non-Referred Group, a Referral Status CRF is needed for each subsequent visit unless the subject is referred to the EP Referred Group. During study follow-up visits, the Non-Referred Group subjects can be referred to the EP Referred Group if their LVEF is $\leq 40\%$ or meets one of the referral criteria (as listed above).

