9.10. Deviation Handling

A study deviation is defined as an event within a study that did not occur according to the Clinical Investigation Plan or the Clinical Trial Agreement.

Prior approval by the Medtronic study manager is expected in situations where the investigator anticipates, contemplates, or makes a conscious decision to deviate. Prior approval is not required when a deviation is necessary to protect the life or physical wellbeing of a subject in an emergency or in unforeseen situations beyond the investigator's control (e.g. subject failure to attend scheduled follow-up visits, inadvertent loss of data due to computer malfunction, inability to perform required procedures due to subject illness, etc.).

For medically justifiable conditions which preempt a subject's ability to complete a study-required procedure, it may be permitted to complete only one deviation Case Report Form which will apply to all visits going forward. This may also apply for other unforeseen situations (e.g. the subject permanently refuses to complete a study required procedure and the data will not contribute to the primary end point analysis, etc.). However, prior approval from Medtronic is required for such situations.

All study deviations must be reported on the Case Report Form regardless of whether medically justifiable, pre-approved by Medtronic, an inadvertent occurrence, or taken to protect the subject in an

emergency. Please refer to the Case Report Form Completion Guideline for the examples of deviations. The deviation must be recorded with an explanation for the deviation and corrective/ preventative action(s).

In the event the deviation involves a failure to obtain a subject's consent, or is made to protect the life or physical wellbeing of a subject in an emergency, the deviation must be reported to the MEC/IRB (where applicable) as well as Medtronic within five (5) working days. Reporting of all other study deviations should comply with MEC/IRB policies and/or local laws and must be reported to Medtronic as soon as possible upon the center becoming aware of the deviation. Reporting of deviations must comply with IRB/ MEC policies, local laws, and or regulatory agency requirements. Refer to Investigator Reports (Table 8) for geography/country-specific deviation reporting requirements and timeframes for reporting to Medtronic and/or regulatory bodies.

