6.1 Sample Size Assessment

The sample size calculation was based on the width of the 95% confidence interval for the proportion of subjects that is referred for SCD risk stratification and management among subjects who have a reason for referral at the 3 months visit. The following assumptions were made:

- Drop-out and mortality rate combined from enrollment to 3 months visit of 10%,
- At the 3 months visit, 30% of subjects will have a reason for referral.

Under these assumptions, enrollment of approximately 200 patients per region is needed, to have at least 80% power to achieve a 95% confidence interval width of 25% when 70% of patients with a reason for referral at the 3 months visit is referred for SCD risk stratification and management.

The sample size has been computed as follows.

First, the number of subjects needed in each region with a reason for referral at the 3 months visit ($N_{\text{reason_referral}}$) was computed using the SAS procedure below:

```
proc power;
onesamplefreq
  ci = wilson
  halfwidth = 0.125
  probwidth = .
  proportion = 0.70
  ntotal = 40 to 70 by 1;
run;
```

where proportion = 0.70 is the proportion of subjects to be referred among those with a reason for referral and halfwidth = 0.125 is half of the 95% confidence interval around this proportion. As a result of the above SAS procedure, the needed number of subjects that will give at least 80% power to achieve a 95% confidence interval of halfwidth = 0.125 around a proportion of 70% of subjects with a reason for referral that will be referred is $N_{\text{reason_referral}} = 54$.

Secondly, the number of subjects expected at the 3 months visit was computed as the ratio between the required number of subjects with a reason for referral at the three months visit ($N_{\text{reason_referral}} = 54$) and the assumed proportion of subjects with a reason for referral at the three months visit ($\text{prop}_{\text{referral_assumed}} = 0.30$) :

$$N_{\text{3months}} = \frac{N_{\text{reason_referral}}}{\text{prop}_{\text{referral_assumed}}} = \frac{54}{0.30} = 180$$

The number of subjects to be enrolled was then computed as the expected number of subjects that will complete the three months visit ($N_{\text{3months}} = 180$) and the assumed proportion of subjects that will not drop-out or die between enrollment and the 3 months visit ($1 - \text{rate}_{\text{exit_assumed}} = 0.90$):

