7.2 General Methodology

Data summaries for categorical data will include count, e.g., number of patients, and/or number of events, and a percentage relative to the total number of patients/events. The denominator will be explicitly identified when not clear from the context. Continuous variables will be represented by mean and standard deviation, except when the distribution of the variable is highly skewed in which case median and quartiles will be reported.

P-values for hypothesis testing will be evaluated based on two-sided testing using significance level of 0.05. Confidence intervals will be reported as two-sided 95% confidence intervals.

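### The re-assessment formula in SAP 6.2 turns completed 3-month visits into enrolment using deaths and drop-outs only, so it cannot see subjects who stay in the study but miss that visit

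*SAP*

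**What the plan says.** SAP 6.1 aims for a Wilson 95% interval of half-width 0.125 around 70% referred, and reports 54 as "the needed number of subjects that will give at least 80% power to achieve a 95% confidence interval of halfwidth = 0.125". It divides 54 by 0.30 to get 180 subjects at the 3-month visit. It then divides 180 by 0.90, described as "the assumed proportion of subjects that will not drop-out or die between enrollment and the 3 months visit", to get 200 enrolled. Protocol 12.2.5 carries the same 10% and 30% assumptions.

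SAP 6.2 repeats the two steps with observed values. The reason-for-referral proportion has as its denominator "Number of subjects with a 3 months visit completed". The exit rate has as its numerator "Number of deaths and drop out before the 3 months visit", over all enrolled. A region may be re-assessed when the exit rate departs from 10% or the reason proportion departs from 30%. The stated aim is to keep at least 80% power for the 25% width.

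On attendance, Protocol 9.6 says that "a late visit is preferred over a missed visit but must be accompanied by a deviation". Protocol 9.10 names "subject failure to attend scheduled follow-up visits" among the situations where a deviation needs no prior approval. The exit reasons in Protocol 9.7 and the exit-form statuses in SAP 7.9.1.3 do not include a missed visit.

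**The concern.** The two steps join only if everyone who neither dies nor drops out completes the 3-month visit. The documents foresee subjects who do not. Such a subject cannot enter the primary denominator, because SAP 7.9.1.3 builds it from the 3-month referral form and Protocol 12.5 rules out imputation. The five 3-month groups in SAP 7.9.1.3 have no place for someone still in the study without a visit.

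Neither monitored quantity reacts to this loss. Missed visits add nothing to the exit rate, and they do not shift the reason proportion if those who miss resemble those who attend. A region could therefore be declared on target while it is short of 54 evaluable subjects. The stated precision would then be wrong for the primary estimate in that region.

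**Working it through.** **Inputs from the documents.** Wilson interval, half-width at most 0.125, probability at least 0.80, true proportion 0.70, 30% with a reason, 10% exits (SAP 6.1). On the level: "Confidence intervals will be reported as two-sided 95% confidence intervals" (SAP 7.2), so z = 1.96.

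**Assumed input.** m is the share of all enrolled who stay in the study but miss the 3-month visit. The documents give no value, so 0%, 2%, 5% and 10% are shown.

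**Step 1: reproduce the plan's figure.** For x referred out of n, with p = x/n, the Wilson half-width is

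h(x, n) = z·√[p(1 − p)/n + z²/(4n²)] / (1 + z²/n).

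The plan's power is the sum of Binomial(n, 0.70) probabilities over every x with h ≤ 0.125:

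| n evaluable | Probability of width ≤ 25% |
|---|---|
| 48 | 0.521 |
| 49 | 0.484 |
| 50 | 0.569 |
| 51 | 0.649 |
| 52 | 0.722 |
| 53 | 0.784 |
| 54 | 0.897 |

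The smallest n reaching 0.80 is 54. Then 54/0.30 = 180 and 180/0.90 = 200. All three figures reproduce. One evaluable subject fewer takes the probability below 0.80.

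**Step 2: what the 6.2 formula returns.** With 10% exits and 30% reasons among completed visits, it gives (54/0.30)/(1 − 0.10) = 200. The symbol m does not appear, so the answer is 200 at any missed-visit rate, and neither trigger is met.

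**Step 3: what 200 enrolled delivers.** Expected evaluable = 200 × (0.90 − m) × 0.30. Enrolment needed to expect 54 = 180/(0.90 − m), rounded up.

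| m (of enrolled) | Expected evaluable at 200 | Probability at that n | Enrolment needed | 6.2 formula |
|---|---|---|---|---|
| 0% | 54.0 | 0.897 | 200 | 200 |
| 2% | 52.8 | 0.722 (n = 52) to 0.784 (n = 53) | 205 | 200 |
| 5% | 51.0 | 0.649 | 212 | 200 |
| 10% | 48.0 | 0.521 | 225 | 200 |

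If m is instead a share of those who have not exited, the need is 180/[0.90 × (1 − m)], which gives 205, 211 and 223 for 2%, 5% and 10%.

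**Step 4: effect on the interval itself.** The mean Wilson width at a true proportion of 0.70 is 23.5% at n = 54, 24.2% at n = 51 and 24.8% at n = 48. The probability falls steeply, but the average interval widens by only about 1.3 points across that range (24.8 − 23.5).

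**The case against.** The best defence is that drop-out is nowhere defined. SAP 6.1 equates the 180 who complete the visit with those who neither drop out nor die, so the planned 10% can be read as all non-completion. That stands for the planning value. It does not clearly rescue SAP 6.2, where the observed quantity is named as an exit rate and SAP 7.9.1.3 ties non-death exits to exit-form statuses. The ambiguity itself needs a sentence.

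The loss may also be small. The window runs from day 40 to day 120, late visits are analysed, and Protocol 9.6 allows follow-up by phone. This limits missed visits without removing them. Late visits are only a partial remedy, because SAP 5.1 counts a referral at an out-of-window 3-month visit at 6 months.

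The protocol evidence is partly indirect. The sentence about keeping the original schedule concerns visits outside the window. That a subject who misses a visit stays in the study is inferred from the exit list, and is not stated outright.

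Finally, the study is descriptive, has no hypothesis and enrols approximately 200 per region, and the average width stays under 25% even at n = 48. That limits the consequence. It does not make the formula right for its stated purpose.

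**Conclusion.** The mismatch is real. Step 1 of SAP 6.2 yields completed visits, Step 2 corrects only for deaths and drop-outs, and a missed visit without exit is in neither. Whenever such visits occur beyond the 10%, the formula returns too small a target and the re-assessment gives no signal. Under the assumed rates of 2%, 5% and 10% of enrolled, the shortfall in enrolment is 5, 12 and 25 per region. These sizes rest on the plan's 10%, 30% and 70%, on missed visits being unrelated to having a reason for referral, and on the probability being read at the expected evaluable number.

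A reader might infer two stronger things. The first is that the stated 80% is simply not delivered. The documents do not support that: at the expected 54 the probability is 0.897, and any shortfall depends on a missed-visit rate they do not give. The second comes from treating the evaluable number as random, which gives about 76% at 200 enrolled with no missed visits at all. That figure reflects chance variation in how many subjects have a reason for referral. It is a separate matter and is no evidence for this point.

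**What to change.** - **SAP 6.2, Step 2.** Replace (1 − observed exit rate) with the observed completion fraction: among enrolled subjects whose 3-month window (day 120) has closed, the share with a completed 3-month visit. Restrict numerator and denominator to the same subjects. Otherwise, visits completed from day 40 by subjects whose window is still open would inflate the fraction during accrual and lower the target.
- **SAP 6.2, trigger.** Re-assess when this fraction differs from 90%, in place of the exit rate differing from 10%. Keep the 30% trigger.
- **SAP 6.1 and Protocol 12.2.5.** State that the 10% means no completed 3-month visit for any reason: death, exit or missed visit.
- **If a region is not extended.** Restate the probability of reaching the 25% width at its actual evaluable number.

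The cost is one formula, one trigger and one assumption sentence, using visit data already collected. At the assumed 2%, 5% and 10%, six regions would need 6 × 205 = 1,230, 6 × 212 = 1,272 or 6 × 225 = 1,350 subjects, all well below the 2,400 maximum in the protocol. The alternative is a less favourable stated probability for the regions affected.

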countries could participate within these geographies. Each geography is expected to enroll approximately 200 subjects, with a total of approximately 1,200 subjects from 6 geographies. The actual sample size may increase up to 2,400 subjects, depending on the observed mortality and drop-out rate between enrolment and three months follow-up and on the observed proportion of subjects with a reason for referral at the three months visit.

[figure not shown]
Prior to study site initiation, current referral information will be collected from sites, and investigators and other site clinical personnel will be provided with educational materials (available under a separate cover) that address the importance of EF measurement and care pathway for post-MI patients.

Methods incorporated in the study design to minimize potential bias include (but are not limited to):

- Subject demographics will be collected at baseline for potentially analyzing differences that may affect the endpoints.
- All study clinicians and Medtronic personnel will be trained on the corresponding aspects of the study using standardized training materials.
- All study clinicians and Medtronic personnel will be trained on and required to follow the Protocol.
- Sites will be encouraged to approach any eligible patients meeting inclusion/exclusion criteria
- Each geography is expected to enroll an approximate 200 subjects to have at least 80% power to achieve a moderate to high number of patients referred for SCD risk stratification and management.
- For each geography, sites where the same physician acts both as an interventional cardiologist and as an electrophysiologist will be limited to a maximum of 20% of the total sites in the geography, and approximately 20% of the total expected enrollments in the geography will be enrolled in these sites.
- To ensure a wide distribution of data between sites, the maximum enrollments per site will be no more than 20% of the total expected enrollment in the geography.

See Figure 1 and Section 9 for further detail on study procedures and data collection as well as timepoints for data collection.

Figure 1 Study Flow

***For patient enrollment:** Patients must be enrolled ≤ 30 days post-acute MI and must have an EF $< 50\%$ measured ≤ 14 days post-acute MI.

****Referral Criteria:** sustained VT, cardiac or unexplained syncope, clinically significant palpitations, new onset bundle branch block, conduction abnormalities, or symptomatic bradycardia.

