12.4. Interim analysis

No interim analysis is planned for this study. However, drop out, mortality rates and reason for referral at the chronic phase visit will be monitored on an ongoing basis to account for possible heterogeneity in drop-out rate, mortality rate and reason for referral across geographies, which may require a different number of patients than expected to be enrolled in certain geographies.

In geographies where the drop-out and mortality rates and the reasons for referral are different than expected, enrollment may continue beyond 200 subjects to account for their specific drop-out rate, mortality rates and reasons for referral, while it may be stopped at approximately 200 subjects in other geographies.

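### SAP 6.2 lets the sample size re-assessment lower a region's target below the protocol's 200 on early, noisy rates, and states 80% power with no floor and no reference to the 2,400 maximum

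*SAP*

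**What the plan says.** SAP 6.1 plans each region on the Wilson interval for the proportion referred among subjects with a reason for referral. The aim is "at least 80% power to achieve a 95% confidence interval width of 25" per cent, which leads to 54 subjects with a reason, 180 at the 3-month visit and 200 enrolled.

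SAP 6.2 then says that rates are monitored continuously and that a re-assessment may be done in regions whose exit rate differs from 10% or whose share with a reason differs from 30%. The requirement stays at "N_{reason_referral} = 54", divided by the observed share and by one minus the observed exit rate. In such regions "the number of subjects to be enrolled will change from the assumed approximately 200" to the result, and the stated purpose is to secure at least 80% power for the 25% width. No tolerance, timing, minimum data, lower limit or upper limit is given.

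Protocol 12.4 describes two outcomes. Where rates differ from expectation, enrolment may go on past 200, "while it may be stopped at approximately 200 subjects in other geographies". Protocol section 6 adds the study-wide limit: "The actual sample size may increase up to 2,400 subjects". The SAP nowhere mentions 2,400.

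**The concern.** The protocol describes a rule that can only add subjects, up to a limit. The SAP describes one that moves both ways without limit. An observed share of 40% with 10% exit gives 54/0.40/0.90 = 150, an outcome that protocol 12.4 does not describe.

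Observed rates almost never equal 10% and 30% exactly, so the trigger filters out very little. A region whose early share is high by luck would have its target lowered, and would then tend to fall short of 54 subjects with a reason. At the other end, a low share can push the formula past what the protocol permits while the SAP still states 80% power. At stake are the point at which each region stops enrolling and the precision of the primary estimate.

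**Working it through.** **Inputs.** From SAP 6.1: Wilson interval, "halfwidth = 0.125", "proportion = 0.70", 10% exit, 30% with a reason. From SAP 7.2: "Confidence intervals will be reported as two-sided 95% confidence intervals". From SAP 6.2: 54 and the update formula. From protocol section 6: six geographies and 2,400. The size of the data set at re-assessment, m, is not in the documents; I take 30 to 150.

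**1. The plan's own figures.** The exact binomial probability that the Wilson half-width is at most 0.125 when the true proportion is 0.70 is 0.784 at n = 53 and 0.897 at n = 54. So 54 is the smallest n that reaches 80%. Then 54/0.30 = 180 and 180/0.90 = 200. The base calculation is correct.

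**2. What the update does by chance.** Let m enrolled subjects all be followed to 3 months, with c completing the visit and r having a reason. Then prop = r/c and 1 − rate = c/m, so the new target is 54m/r. If the planning values are true, r is binomial with size m and probability 0.30 × 0.90 = 0.27. The target falls below 200 when r/m is slightly above its expected value, which happens in roughly half of samples. At m = 100 the chance of observing exactly 10% and 30%, so that the trigger is not met, is about 0.012.

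**3. Probability of a width of at most 25%.** For each r, I enrol up to the new target, draw the remaining subjects with a reason at probability 0.27, and average the probability from step 1 over the final number.

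| m | target < 200 | target < 180 | as written | floor of 200 |
|---|---|---|---|---|
| 30 | 0.42 | 0.28 | 0.70 | 0.90 |
| 50 | 0.49 | 0.26 | 0.74 | 0.90 |
| 60 | 0.46 | 0.25 | 0.75 | 0.90 |
| 100 | 0.45 | 0.21 | 0.80 | 0.91 |
| 150 | 0.49 | 0.18 | 0.86 | 0.92 |

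The comparator is a fixed 200 with no re-assessment, which gives 0.76 because the number with a reason varies around 54. Among regions cut below 200, the probability as written is 0.52 (m = 50), 0.55 (m = 60) and 0.68 (m = 100).

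**4. How much wider.** If a region is cut to 150 by luck, the expected number with a reason is 150 × 0.27 = 40.5. The Wilson half-width at 0.70 with n = 40 is 1.96 × √(0.21/40 + 3.84/6,400)/(1 + 3.84/40) ≈ 0.137, a width of about 27% against the intended 25%.

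**5. The maximum.** 2,400/6 = 400 per region on average, reached when prop × (1 − rate) = 54/400 = 0.135. That is half the planned 0.27; at 10% exit it means a share of 15%. At a 12% share the formula asks for 54/0.12/0.90 = 500. Held to 400, the region yields 400 × 0.12 × 0.90 ≈ 43 subjects with a reason, and the probability of the target width is about 0.21. Under the planning values, the chance that the six targets together exceed 2,400 is below 0.0001.

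**The case against.** Several stronger readings are tempting, and the documents do not support them.

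- **That about half of all regions will be cut.** The SAP says a re-assessment may be performed. The 42–50% applies only where one is run, once, before 200 are enrolled. Many cuts are small against a target that is itself approximate. If 200 subjects accrue evenly over 12 months, about 50 are enrolled in any 3 months, so by m = 150 all 200 are in and no cut is possible.
- **That the SAP breaches a stated protocol minimum.** Protocol 12.4 is permissive and states no minimum, and the synopsis says that numbers may vary by geography. The floor is implied by the two outcomes described.
- **That the rule is worse than having no re-assessment.** It is clearly worse only at very early looks. At m = 60 it is about level with a fixed 200 (0.75 against 0.76), and from about m = 80 it is better (0.78).
- **That the study may exceed 2,400 by chance.** It will not; the true yield would have to be half the planned one.

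It is also fair to say that the floor gains precision by enrolling more subjects: a fixed 220 already gives about 0.91. And where a region truly has a 40% share, 150 subjects are enough to expect 54 with a reason.

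These points limit the size of the problem but do not remove it. Nothing in SAP 6.2 separates a truly high share from early noise, and the 80% statement carries no condition.

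**Conclusion.** The point holds in limited form. SAP 6.2 permits downward changes that protocol 12.4 and section 6 do not describe, and its 80% statement is not supported for early re-assessments (0.70 to 0.78 for m of about 30 to 80) or where the 2,400 maximum binds. After an early cut, the chance of the intended width is only about 0.52 to 0.68 (m = 50 to 100). The practical loss is a regional interval a few percentage points too wide; there is no hypothesis test to invalidate. These figures assume that the planning values are true, that there is one look, and that both rates come from the same m subjects. The maximum is a separate, conditional matter that arises only if prop × (1 − rate) averages below 0.135.

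**What to change.** In SAP 6.2, set the regional target to max(200, `N_enrolled_update`), subject to the protocol's total of 2,400, so that a re-assessment can only raise a target, as protocol 12.4 describes. Where the maximum binds, replace the 80% statement with the CI width expected at the capped number. Stating when the re-assessment is done, or the minimum 3-month data it needs, would help further.

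This is a wording change to the SAP. Compared with the rule as written, it adds about 9–17 subjects per region on average under the planning values (for example 224 against 210 at m = 60), within the 2,400. Regions with a truly high share would enrol the planned 200 where the present formula would allow fewer.
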